### **Missing Data**

All available data of the subjects who withdraw from the study for any reasons will be analyzed. Missing data will be assumed to be missing at random. There will be no imputation of missing data for the analysis purpose. Change from baseline of an endpoint will be missing when either baseline value of the endpoint is missing or post-baseline value of the endpoint is missing.

Incomplete start and end dates for adverse events and concomitant medications are imputed as follows:

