### **4.2. Intent-to-Treat (ITT) Population**

The Intent-to-Treat (ITT) Population will include all randomized patients who received any amount of IP (OCA or placebo). The ITT Population will be the primary population used for summarizing efficacy and pharmacodynamic analyses assessments. Subjects will be analyzed according to randomized treatment.

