### 9.3. Liver Biochemistry and Hepatobiliary Damage

Liver biochemistry includes total and direct bilirubin, ALP, ALT, AST, and GGT, INR, creatinine, albumin, and platelets.

- Summary statistics of liver biochemistry including baseline values, change from baseline, and percentage change from baseline values will be provided by treatment group and by each scheduled post-baseline visit.
- Change from baseline will be analyzed by using an ANCOVA model with change from baseline as the dependent variable, treatment group and randomization stratification factor as fixed effects and the baseline value as a covariate.
- Percent change from baseline will be analyzed by using an ANCOVA model with percent change from baseline as the dependent variable, treatment group and randomization stratification factor as fixed effects and the baseline value as a covariate.
- As a sensitivity analysis, change from baseline and percent change from baseline of liver biochemistry parameters will be analyzed by using a restricted maximum likelihood (REML) based MMRM. Treatment group, time, treatment group by time interaction, and randomization stratification factor will be included as fixed effects and parameter baseline values will be included as a covariate in the model, where time includes all post baseline visits of DB phase.
- An unstructured covariance structure will be used to model the within-participant errors. If there is a convergence issue with the unstructured covariance model, Toeplitz, Autoregressive (1) (AR (1)) covariance structure will be used, following this sequence until convergence is achieved. If the model still does not converge with AR (1) structure, no results will be reported. When the covariance structure is not unstructured, the sandwich estimator for the variance-covariance matrix will be derived, using the EMPIRICAL option in the PROC MIXED statement in SAS. The p-value will be interpreted at 0.05 level of significance.
- The tabulation of ANCOVA model and MMRM model will include estimates of least-square (LS) means, SEs, and 2-sided 95% CIs for each treatment group. Estimates of the mean difference, SE of the difference, 2-sided 95% CI of the difference between treatment groups, and p-value will also be presented.

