### 9.6. Clinical Outcome Events

The following clinical outcome events will be captured in the study:

- Time from first dose to death (all cause)
- Time from first dose to liver-related death
- Time from first dose to liver transplant
- Time from first dose to MELD score  $\geq 15$  (for patients with MELD  $\leq 12$  at baseline)
- Time from first dose to earliest hospitalization for new onset or recurrence of:
  - variceal bleed
  - hepatic encephalopathy (as defined by a West Haven score of  $\geq 2$ )
  - spontaneous bacterial peritonitis (confirmed by diagnostic paracentesis)
- Time from first dose to uncontrolled ascites (diuretic resistant ascites requiring therapeutic paracentesis at a frequency of at least twice in a month)
- Time to first occurrence of any above listed clinical events

The incidence and time to first occurrence of any above listed clinical events will be summarized by treatment group using the log rank test stratified by the randomization stratification factor. The minimum and maximum time to clinical event will be presented. KM estimates of the

distribution of the time-to-event will be tabulated and graphed by treatment group. The tabulation will include the KM methodology using 25th, 50th (median), and 75th percentiles with associated 2-sided 95% CIs, as well as percentage of censored observations. The number and percent of patients censored and with events will be presented. The hazard ratio and 2-sided 95% CI will be estimated based on a Cox regression model stratified by randomization strata. The proportionality of hazards will be assessed using Schoenfeld residuals.

In addition, the incidence and time to each of the above clinical events, and the incidence and time to occurrence of HCC will be summarized by treatment group using the same methods as defined above.

For the time to event analyses, subjects who do not experience an event will be censored at the time of their last contact. Subjects with no data after randomization will be considered to have an event on Day 1 (first day of IP dosing). All time-to-event endpoints include only adjudicated events.

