### 10.3.3. Adverse Events of Special Interest

The following decompensation events are adverse events of special interest:

- Variceal bleeding or recurrent variceal bleeding documented by endoscopy OR patient presenting with anemia or melena (hemoglobin drop  $\geq 2$  g/dL) and found to have varices documented by endoscopy, irrespective of hospitalization or requirement of blood transfusion.
- Gastrointestinal bleeding as a result of gastric or duodenal varices verified by endoscopy
- Hepatic encephalopathy, Grade  $\geq 2$
- New onset ascites requiring treatment
- Worsening of ascites (requiring increase in drug therapy or requirement of surgical procedure such as paracentesis or shunt placement)
- Refractory ascites -unresponsive to medications, and patient is not a candidate for TIPS or shunt and requires large volume paracentesis
- Hyponatremia ( $\text{Na} \leq 125$  mEq/L) secondary to ascites
- Spontaneous bacterial peritonitis (confirmed by diagnostic paracentesis- by cell count/chemistry)

- Hepatorenal syndrome Type 1 and Type 2 and Acute Kidney Injury (AKI)
- Liver failure defined as worsening of liver synthetic function that is persistently worse relative to baseline and/or progressive over time:
  - Hepato-pulmonary syndrome
  - Porto-pulmonary syndrome
  - Liver Transplant
  - Increase in MELD scores by 3 points relative to baseline, persistent over time and unrelated to vitamin K deficiency related increase in INR
  - Any liver related event that requires hospitalization and treatment

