### Baseline and Change from Baseline

The baseline value for statistical analyses of quantitative parameters is defined as the mean of all available evaluations prior to the first administration of IP, unless otherwise specified. Values collected at unscheduled visits prior to the start of the IP administration will be included in the calculation of baseline values. If there is only one evaluation prior to the first administration of IP then the available data from this evaluation will be used as the baseline value.

The baseline value for analyses of lipid parameters is defined as the last fasted evaluation prior to the first administration of IP.

The baseline value for analyses of qualitative parameters (eg, normal/abnormal) is defined as the last evaluation prior to the first administration of IP.

Baseline values defined above will not change regardless if a subject stops taking IP and begins taking commercially marketed OCA.

Change from baseline = (post-baseline value – baseline value).

Percent change from baseline =  $100 * (\text{post-baseline value} - \text{baseline value}) / \text{baseline value}$

For the purpose of tabulations, the unscheduled post-baseline values generally will be excluded from summary tables, but will be included in data listings. Unscheduled visits will be considered for analyses of shift from baseline to worst value (low-normal-high).

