## **Visit Windows**

Visit windows are specified in the Table 1 of the protocol - Schedule of Study Procedures for the 2 phases of the study: DB phase and DBext phase. All data will be tabulated per the evaluation visits as recorded on the electronic case report form (eCRF) even if the assessment is outside of the visit window. In data listings, the study day of all dates will be presented. Data collected at unscheduled visits that occurred outside the time windows specified will be included in the data listings but will not be included in the analyses unless otherwise stated.

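### The SAP sets no cut-off at liver transplant, so donor-liver values, if collected at scheduled visits, enter the efficacy change-from-baseline analyses, usually as improvement

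*SAP*

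**What the plan says.** **Transplant is foreseen.** It is an exploratory clinical event (Section 2.1.3) and a time-to-event outcome, "Time from first dose to liver transplant" (Section 9.6). In Section 10.3.3 it is an adverse event of special interest, listed under the item that begins "Liver failure defined as worsening of liver synthetic function that is persistently worse relative to baseline and/or progressive over time".

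**Which values are analysed.** Efficacy and pharmacodynamic analyses use everyone randomized and dosed (Sections 4.2, 9 and 12), with no on-treatment restriction. Appendix A, Missing Data, says "All available data of the subjects who withdraw from the study for any reasons will be analyzed" and "There will be no imputation of missing data for the analysis purpose", with missing data assumed to be missing at random. Appendix A, Visit Windows, tabulates data by the visit recorded on the eCRF. For liver biochemistry, Section 9.3 says "Change from baseline will be analyzed by using an ANCOVA model with change from baseline as the dependent variable", with an MMRM as sensitivity analysis. MELD and Child-Pugh are compared by Wilcoxon rank sum test with a Hodges-Lehmann estimate and also shown in shift tables (Sections 9.1 and 9.2).

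**Data after stopping treatment.** Section 5 reports completion of the study separately from completion of treatment. Appendix A adds "Baseline values defined above will not change regardless if a subject stops taking IP and begins taking commercially marketed OCA".

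**Exclusions that are written.** The SAP excludes non-fasted pharmacodynamic samples (Section 12.3.1), certain pharmacokinetic data (Section 11.3) and, in general, unscheduled values (Appendix A). None of these exclusions concerns transplant.

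**The concern.** Bilirubin, INR, albumin, MELD, Child-Pugh, stiffness and ELF measured after a transplant describe the donor liver. Subtracting the native-liver baseline from them gives a change that says nothing about study treatment. If the graft works, that change is usually a marked improvement. The same patient would then be a failure in Section 9.6 and a responder in Sections 9.1 to 9.5, and an arm with more transplants would tend to look better on liver function.

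The event is plausible here: all patients are Child-Pugh B or C, at least 20% are to be class C, and double-blind treatment runs from 48 weeks to roughly 3 years. The SAP lists ICH E9(R1) among its references but states no strategy for transplant or any other intercurrent event.

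**Working it through.** **1. Where such values could enter**

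| Analysis | Reach of the SAP text | Post-transplant value enters? |
|---|---|---|
| Efficacy summaries; MELD and Child-Pugh shift tables (9, 9.1, 9.2) | scheduled visits, extension included | Yes, if collected |
| ANCOVA, MMRM, MELD and Child-Pugh rank tests (9, 9.3) | double-blind-phase visits | Only for a transplant before Week 48 |
| Bile acids, C4, FGF-19 (9.4, 12) | pre-dose samples from patients confirmed fasting (12.1, 12.3.1) | Only if the sample meets those rules |
| Safety laboratory summaries (10) | to treatment discontinuation + 30 days | Only within that window |
| Unscheduled values (Appendix A) | generally listed only | Generally no |

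**2. Sample size.** Section 3.3: 20 + 10 + 20 = 50 patients, as the SAP states. With 1:1 allocation, 50/2 = 25 per arm.

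**3. Child-Pugh (SAP Table 2, minimum score 5).** A return to 5 gives 5 - 7 = -2, 5 - 9 = -4, 5 - 10 = -5 and 5 - 15 = -10. Each is the largest improvement possible from its baseline, and each appears in the shift table as B to A or C to A.

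**4. MELD.** The SAP does not print the formula. Assumed: 3.78 ln(bilirubin) + 11.2 ln(INR) + 9.57 ln(creatinine) + 6.43, in mg/dL, inputs below 1 set to 1. The profiles are also assumptions.

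- Baselines (bilirubin / INR / creatinine): 2 / 1.2 / 0.9 gives 11.1; 3 / 1.3 / 0.9 gives 13.5; 5 / 1.6 / 1.0 gives 17.8.
- After transplant, bilirubin 0.8 and INR 1.0: 6.4 with creatinine 0.9, 8.9 with 1.3, 12.1 with 1.8.
- Falls to 6.4: 4.7, 7.1 and 11.4 points. With creatinine 1.8, the baseline of 11.1 instead rises by 1.0.

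**5. Bias in the treatment comparison.** Assumptions: 25 per arm, no true effect, normal changes with SD 1, negative meaning improvement. The worst one or two patients in one arm are transplanted, and their value becomes an improvement of 1, 2 or 3 SD (3,000 simulated trials for each setting).

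| Transplants | Mean difference at 1 / 2 / 3 SD | Hodges-Lehmann at 1 / 2 / 3 SD | Mean difference if the values are dropped |
|---|---|---|---|
| 1 | -0.12 / -0.16 / -0.20 | -0.11 / -0.13 / -0.14 | about -0.08 |
| 2 | -0.21 / -0.30 / -0.38 | -0.20 / -0.26 / -0.27 | about -0.15 |

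Check for one transplant: a mean of -0.082 after dropping the patient implies a worst value of 0.082 × 24 = 1.97 SD. Replacing it by an improvement of d shifts the mean by -(1.97 + d)/25, which is -0.12, -0.16 and -0.20 for d = 1, 2 and 3.

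The transplanted patient's median rank in the arm is 1st at an improvement of 2 or 3 SD and 5th at 1 SD.

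**6. What exclusion alone achieves.** With one transplant, 0.08/0.20 = 40% to 0.08/0.12 = 67% of the bias remains, because a failing patient drops out of the comparison under a missing-at-random rule with no imputation.

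**The case against.** The strongest reply is that inclusion is inferred from silence. The all-available-data sentence is about patients who withdraw and does not mention transplant. The fixed-baseline sentence concerns a switch to commercial OCA, and censoring at last contact in Section 9.6 does not show that laboratory or elastography visits continue. Whether such visits exist depends on the protocol, which is not at hand. If transplant ends participation, there are no donor-liver values to exclude, and what remains is informative dropout. This stands, and it makes the point conditional on collection. It does not remove the gap: how to treat post-transplant values is an analysis rule, and the SAP's general rules would admit them.

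A reader might infer that these values stay in every change-from-baseline analysis and that the patient is always among the arm's best. The SAP does not support that. Safety summaries stop 30 days after treatment, unscheduled values are generally left out, the models and the MELD and Child-Pugh tests stop at the double-blind phase, and pharmacodynamic samples must be pre-dose and fasting. The patient's rank depends on the parameter and on graft function, and MELD can fail to improve if creatinine is raised.

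A reader might also picture a fall from MELD 20 to 8, or a shift of -12/5 = -2.4 points in a Child-Pugh C stratum of five per arm. The SAP gives no basis for a MELD of 20, change is taken from trial baseline rather than from just before transplant, and no analysis of MELD within class C is planned.

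Finally, Section 2.2 tests no formal hypothesis, the endpoints are secondary or exploratory, rank methods limit one patient's influence, and transplants are reported openly elsewhere. All of this stands and limits the importance.

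**Conclusion.** The point holds in conditional form. The SAP foresees transplant, has no cut-off at it, and would carry scheduled post-transplant values into the efficacy summaries, the shift tables and, before Week 48, the models and rank tests.

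For one transplant the illustrated bias is about -0.12 to -0.20 SD in the mean and -0.11 to -0.14 SD in the Hodges-Lehmann difference, favouring the arm where it happened. This rests on 25 per arm, a patient who would otherwise be the arm's worst, and a post-transplant improvement of 1 to 3 SD. The SAP gives no transplant rate; with no transplant, or no later values, the effect is zero.

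The repair is worth making because it is cheap and prevents a failure being read as benefit. The gap does not touch the pharmacokinetic objective, and safety summaries are largely protected by their 30-day limit.

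**What to change.** Add to Appendix A, with cross-references in Sections 9.1 to 9.5 and Section 12: *Values collected on or after the date of liver transplant are listed only. They are excluded from change-from-baseline summaries, shift tables, ANCOVA, MMRM and rank analyses. The number of subjects affected is footnoted by treatment group. Transplant remains an event in Section 9.6.*

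Since exclusion leaves part of the bias, also add to Sections 9.1 and 9.2 a supportive Wilcoxon analysis of MELD and Child-Pugh that assigns the worst rank at visits after transplant or death.

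The cost is a short SAP addition, a date filter, slightly fewer late observations and one extra supportive run.

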#### **Incomplete Start Date:**

##### *Missing day and month*

- If the year is the same as the year of the first dosing date, then the day and month of the first dosing date will be assigned to the missing fields.
- If the year is prior to the year of first dosing date, then December 31 will be assigned to the missing fields.
- If the year is after the year of first dosing, then January 1 will be assigned to the missing fields.

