### 10.3.1. Treatment-emergent Adverse Events

An AE is defined as a treatment emergent adverse event (TEAE) if it meets one or more of the following criteria:

- An AE starting on or after the first study drug dose and within 30 days after the last dose of study drug.

- An AE occurring prior to the first study drug dose that worsens (increase in grade) after the first study drug dose.

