## 10.8. Concomitant Medications

Concomitant medications are medications that were started after the initial dose of investigational product. Concomitant medications will be mapped to Anatomic Therapeutic Chemical (ATC) class and preferred term using WHO Drug Dictionary Global B3 version, March 2021 and summarized by ATC class, preferred term, and treatment in the Safety population. Summaries will be ordered by descending order of incidence of ATC class and preferred term within each ATC class. Summary will be tabulated for the DB phase, DBext phase, and combined.

Subject with prior and concomitant medications will be presented in a data listing. Prohibited concomitant medications will be flagged in concomitant medication and presented in a data listing.

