##### *Missing day only*

- If the month and year are the same as the year and month of first dosing date, then the first dosing date will be assigned to the missing day.
- If the year of the partial date is before the year of the first dosing date or the year of the partial date and the first dosing date are the same but the month of partial date is

before the month of the first dosing date, then the last day of the month will be assigned to the missing day.

- If either the year of the partial date is after the year of the first dosing date or the year of the partial date and the first dose date are the same but the month of partial date is after the month of the first dosing date, then the first day of the month will be assigned to the missing day.
- If the stop date is not missing, and the imputed start date is after the stop date, the start date will be imputed by the stop date.

*Missing day, month, and year*

- No imputation is needed.

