**Incomplete End Date:**

If the imputed stop date is before the start date, then the imputed stop date will be equal to the start date.

*Missing day and month*

- If the year of the incomplete stop date is the same as the year of the last dosing date, then the day and month of the last dosing date will be assigned to the missing fields.
- If the year of the incomplete stop date is prior to the year of the last dosing date or prior to the year of the first dosing date, then December 31 will be assigned to the missing fields.
- If the year of the incomplete stop date is prior to the year of the last dosing date but is the same as the year of the first dosing date, then the first dosing date will be assigned to the missing date.
- If the year of the incomplete stop date is after the year of the last dosing date, then January 1 will be assigned to the missing fields.

*Missing day only*

- If the month and year of the incomplete stop date are the same as the month and year of the last dosing date, then the day of the last dosing date will be assigned to the missing day.
- If either the year of the partial date is not equal to the year of the last dosing date or the year of the partial date and the last dosing date are the same but the month of partial date is not equal to the month of the last dosing date, then the last day of the month will be assigned to the missing day.

*Missing day, month, and year*

- No imputation is needed.

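### The check that an imputed start date cannot fall after a known stop date is printed only for a missing day, so a year-only adverse event that ended before dosing can count as treatment-emergent

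*SAP*

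**What the plan says.** Appendix A (Missing Data) sets the scope: "Incomplete start and end dates for adverse events and concomitant medications are imputed as follows". The start-date rules then come in blocks, by how much of the date is missing.

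- **Missing day and month.** If the recorded year is the year of first dose, "then the day and month of the first dosing date will be assigned to the missing fields". An earlier year gives 31 December and a later year gives 1 January. Nothing in this block refers to the stop date.
- **Missing day only.** Three bullets compare the partial month and year with the first dose date. The last bullet is a consistency check. It begins "If the stop date is not missing, and the imputed start date is after the stop date" and in that case replaces the start with the stop date.
- **Incomplete End Date.** A matching check stands above all of that section's sub-headings: "If the imputed stop date is before the start date, then the imputed stop date will be equal to the start date". It changes an imputed stop date only.

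Section 10.3.1 counts as a TEAE "An AE starting on or after the first study drug dose and within 30 days after the last dose of study drug". Section 10.3.4 restricts all adverse event summaries to TEAEs. Sections 10.3.5 and 10.3.6 add time-to-onset and event-day analyses for pruritus and fatigue.

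**The concern.** The check is missing where imputation can move a date furthest. A missing day moves a start by less than a month; a missing day and month can move it by most of a year. A start set to the first dose date always meets the onset condition for a TEAE, even when the recorded stop date shows that the event was over before dosing. The end-date check does not help, because the stop date here is known and not imputed.

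Safety and tolerability form one of the two primary objectives (Section 2.1.1), and all adverse event tables are built on the TEAE flag. For pruritus or fatigue, such a record would also be an event on Day 1 in the Kaplan-Meier estimates and could put a negative term into the event-day total.

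**Working it through.** The SAP prints no figure on this point, so there is nothing to reproduce. The check applies the rules as printed to assumed dates, then applies them again with the stop-date check extended to year-only starts.

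**Inputs from the SAP**
- Year-only start in the first-dose year: start = first dose date. Year-only start in an earlier year: start = 31 December (Appendix A).
- TEAE if start is on or after first dose (Section 10.3.1, first criterion).
- Day of first dose = study day 1 (Appendix A, Study Day).
- Time to onset = onset date - first dose date + 1 (Sections 10.3.5 and 10.3.6).

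**Assumption.** The SAP gives no formula for event duration. I use stop - start + 1, in line with its other day counts.

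| First dose | Recorded start | Recorded stop | As printed: start, duration, TEAE | With check: start, duration, TEAE |
|---|---|---|---|---|
| 15 Sep 2020 | 2020 | 1 Sep 2020 | 15 Sep 2020, -14 + 1 = -13 days, yes | 1 Sep 2020, 1 day, no |
| 2 Mar 2020 | 2020 | 20 Feb 2020 | 2 Mar 2020, -11 + 1 = -10 days, yes | 20 Feb 2020, 1 day, no |
| 15 Sep 2020 | 2020 | 1 Oct 2020 | 15 Sep 2020, 16 + 1 = 17 days, yes | 15 Sep 2020, 17 days, yes |
| 15 Sep 2020 | 2019 | 1 Jun 2019 | 31 Dec 2019, -213 + 1 = -212 days, no | 1 Jun 2019, 1 day, no |

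Rows 1 and 2 show the fault: the event is flagged as a TEAE with time to onset of 1 day and a negative duration. Row 3 shows that the check changes nothing when the event ran past the first dose. Row 4 shows that an earlier-year start can also land after its stop, although it does not become a TEAE.

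**Same event, one more date part known.** Take row 1, but with the start recorded as September 2020. The *Missing day only* block first assigns 15 September, because month and year match the first dose. Its last bullet then moves the start back to 1 September, and the event is not a TEAE. The plan therefore classifies the same event in opposite ways depending only on whether the month was recorded.

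**Size of one record.** About 50 patients randomized 1:1 (Section 3.3) gives about 25 per arm. One patient wrongly counted in a category moves that arm's incidence by 1/25 = 4 percentage points, if the patient has no other TEAE in that category.

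**The case against.** The strongest reply is that the check already covers this case. Its wording is general: unlike the other bullets in its block, it does not test month or year. Only the block for a wholly missing date follows it, and there nothing is imputed. A programmer could apply it to every imputed start. That may well have been the intent, but the placement says otherwise, and the end-date section shows that the authors put a general check above the sub-headings when they wanted one there. The point is a drafting gap, and it stands as that.

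The second reply is that such records will be rare, and this also stands. Section 3 puts screening at least 14 and not more than 28 days before Day 1. The SAP does not say when adverse event collection starts. If it starts at screening (an assumption), an affected event must have ended no more than 28 days before first dose, so the duration is no lower than -28 + 1 = -27 days. The record would also need a known stop date and an onset known only to the year, while the patient was under observation. A reader might infer errors of several months: a stop on 20 May with first dose on 15 September gives -118 + 1 = -117 days. The arithmetic is right, but the event would have ended well before screening. Section 8 treats diseases that occurred before dosing as medical history, which is outside these date rules.

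A reader might also infer that stopped drugs are reclassified, since the rules cover medications too. The SAP does not support that. Section 8 defines prior medication by when it was taken, and a known stop before dosing settles that whatever start is imputed. Section 10.8 says: "Concomitant medications are medications that were started after the initial dose of investigational product". A start imputed to the dosing date is not plainly after the initial dose.

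Nor are patient-years affected. Section 10.3.4 computes them from the first dose date and the end-of-study date.

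Finally, the adverse event listings show original dates, so an affected record can be found by eye. That helps detection but does not correct the tables.

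**Conclusion.** The point holds for adverse events, as a minor correction. Following Appendix A as laid out, a year-only start in the first-dose year combined with a recorded stop before first dose gives a TEAE with Day 1 onset and a stop date before its start. That classification contradicts the recorded data.

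The result rests on reading the check as belonging to the block in which it is printed. The negative durations also rest on the assumed day count, and a negative term in the pruritus or fatigue event-day totals is an inference, because the SAP does not define how those days are computed.

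Few records are likely to be affected and the SAP gives no count. The effect on the overall safety conclusions is probably small, although a single patient can move an incidence by about 4 percentage points in arms of this size. Nothing is claimed for medications or for patient-year denominators.

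**What to change.** In Appendix A, move the existing check from *Missing day only* to directly under *Incomplete Start Date*, above the sub-headings, as is already done for end dates. Wording: if the stop date is not missing and the imputed start date is after it, the start date is set to the stop date; this applies to every imputed start date.

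The cost is moving one sentence before the SAP is finalized, plus confirming that the imputation program applies the check to year-only starts. No new rule is added, and records whose stop date falls on or after the imputed start are unchanged.
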